5.9 Outcome Assessments – Surveys (Table 1) and Biochemical Samples (Table 2)

Follow up surveys: (Table 1) See Page 32 for full table. A brief follow up survey will be sent to participants through a REDCap-enabled Twilio survey link via email/text message based upon participants preference as stated at enrollment. The surveys will be sent to participants at approximately 1, 3, 6, and 12 months after study enrollment. For completeness, smoking status and medication usage outcomes will be assessed at all follow-up time points. Participants who do not respond to survey invites sent through email or text will be contacted by phone and mail. If the participant cannot complete the follow up survey remotely, we will make all efforts to coordinate with the patient during any pending appointments at VUMC so they can complete their survey on a day when they are already scheduled to be at VUMC (e.g. study RA will travel to the One Hundred Oaks clinic of other VUMC clinics to meet participant) If these modes are insufficient to complete surveys, alternative contacts (participant's proxy) will be contacted. When needed, , study staff call participants to administer the survey, making approximately 24 attempts over 4 to 8 weeks. If unsuccessful, participants may be mailed an abbreviated survey containing only the primary and secondary outcome measures. We have successfully administered similar questionnaires for prior studies of hospitalized smokers and low-income smokers residing in the Mid-South. Mid-Atlantic, and New

England regions. Study staff also offer to meet participants at their clinic visits for convenience. Study staff may also extract information from the EHR fields such as smoking status and cigarettes per day, use of other tobacco products, and smoking cessation medication use.

Biochemical Samples

Aim 1: Biochemical Verification of Self-Reported Abstinence (Table 2, Row 1) For participants who self-report abstinence at the 6 month and/or 12 month follow up surveys, study staff will attempt to biochemically-verify the self-report. Based on prior experience with challenges in obtaining biochemical verification, there will be several options including: (1) saliva cotinine (in- person or mailed); (2) end-expired carbon monoxide (in-person or remote) if participants are unwilling or unable to verify with cotinine (e.g., actively using NRT). Standard saliva cotinine kits will be analyzed by Salimetrics Laboratory or other comparable lab. Smoking abstinence can also be confirmed through in-person or remote carbon monoxide (CO) testing (if a participant is on NRT). If a participant is unable to complete an in-person CO, then a personal CO device (such as a CoVita iCO Smokerlyzer) may be mailed to the participant to complete the CO reading remotely. We have successfully used this protocol for mailed cotinine samples and CO testing in the past. Smoking abstinence will be defined conservatively according to recommended standards. The following cessation milestones will be assessed in addition to point prevalence abstinence (PPA):

- i. *Initial abstinence* is defined as the first instance in which the participant refrains from smoking for at least 24 hours; duration of initial abstinence will also be assessed.
- ii. *Initial lapse,* defined as the first episode of ANY smoking, even a puff, after achieving initial abstinence, will also be assessed.
- iii. Continuous abstinence is defined as no smoking, even a puff, since study enrollment (i.e., achieved PPA at 1, 3, 6, and 12 mo +no smoking in between surveys + biochemical validation of selfreported (SR) PPA at 6, 12 mo). Participants who are unable to biochemically verify abstinence will be assumed to be smoking, by convention, but sensitivity analyses will consider a range of possible odds ratios (1, 2, and 5) linking loss to follow-up and smoking. [51]

| Table 2: Main Ou | itcome Measures by Study | y Aim | | | | |
|-----------------------------------|--|--------------|---|--|--|--|
| Outcome | Measure | Data sources | | | | |
| | | Survey | Other source | | | |
| AIM 1: | SR at 1, 3, 6, 12 m | | | | | |
| Abstinence | Biochem. validation at 6 m (primary study | Х | 12 m* via saliva cotinine <10 ng/ml or expired CO <10ppm | | | |
| AIM 2. | SR at 1 3 6 12 m | | | | | |

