Beginning at approximately 3 days and weeks 2, 4, 6, 8, 10, and 12 post-enrollment the participant will receive automated Interactive Voice Response **(IVR) support calls from TelASK** to assess smoking status and medication receipt/adherence. Participants may also opt to speak with a **study Tobacco Treatment Specialist** if needed. At 6 months, all participants (regardless of smoking status) will be offered a second cycle of IVR calls. To maintain the study timeline, participants recruited in the final year of the study will not be offered the second cycle of IVR calls.

3. Outcome ascertainment

At approximately 1-, 3-, 6-, and 12-months participants will complete **follow up surveys** via:

- Text message or email, based on the participant's preference, containing a link to the REDCap follow up survey. If the participant prefers phone contact, a study team member will call. Compensation is \$20 per completed survey. If participants fail to respond to 6, 12 month surveys, they may be contacted by phone call or mailed survey.
- If the participant cannot remotely complete items related to follow up. including surveys, we will make all efforts to coordinate with the patient during any pending appointments at VUMC so they can complete their

survey on a day when they are already scheduled to be at VUMC (e.g. study RA will travel to the One Hundred Oaks clinic of other VUMC clinics to meet participant).

When study staff is unable to reach participants for follow up surveys after several attempts, the next step will be to reach out to alternative contacts provided by the participant at enrollment. An alternative contact that is a reliable close relative (i.e., spouse, significant other, or caregiver) can opt to complete a survey on the participant's behalf as a proxy. This survey will be considered complete "by-proxy" in the study database.

Biochemical Validation of self-reported tobacco abstinence at 6 and 12 months.

• Participants are asked to complete a carbon monoxide (CO) test or salivary cotinine test to confirm quit smoking status if they indicate on the survey that they have quit smoking. \$100 will be offered for completion of biochemical validation at each of the 6 and 12 month timepoints. \$50 will be offered for travel reimbursement at each of the 6 and 12 month timepoints if patients complete biochemical validation in person.

Compensation. Total compensation for full study participation is \$430.00.

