9.0 Statistical Considerations

9.1 Aim 1

The primary study outcome is biochemically-verified self-reported 7-day point prevalence abstinence at 6 months as defined by salivary cotinine level < 10 ng/ml or expired CO <10 ppm. A secondary outcome is biochemically-verified self-reported 7-day point prevalence abstinence at 12 months. Brief surveys will be conducted at 6 and 12 months after study enrollment to determine self-reported abstinence. Biochemical validation of smoking status is accomplished via mailed salivary cotinine samples or expired CO.

Analysis:

The effect of MIST vs. UC on biochemically-verified abstinence at 6 months will be estimated via a relative risk of abstinence and tested at a 5% significance level via a chi-squared test with Yates' continuity correction. The same method will be applied

to the secondary outcome at 12 months. Anticipated loss to follow up is accounted for in the expected approximate UC abstinence rates where persons lost to follow up will be treated as non-abstinent. However, sensitivity analyses will consider a range of possible odds ratios (1, 2, and 5) linking loss to follow-up and smoking. [51] Exploratory analyses testing for effect heterogeneity will use multivariate logistic regression models adjusting for the main effect of a potential modifier and testing for an interaction with the effect of MIST. The potential effect modifiers to be explored are age, race, sex, NMR, and pre-intervention plan to quit.

Power:

Conservatively assuming a biochemically validated abstinence rate of 10% under UC, a chi-squared test on 1000 patients (at 6 months) will detect a MIST abstinence rate of 16.2% (Risk Difference=6.2%, Relative Risk=1.62, Odds Ratio=1.74) with 80% power. Assuming a 15% biochemically validated abstinence rate under UC (at 12 months), a 22.2% rate under MIST (RD=7.2%, RR=1.48, OR=1.62) is detectable with 80% power. Power was estimated via simulating 20K datasets under the settings above in the statistical program R and were checked against the simplified estimates of the pwr package.

9.2 Aim 2

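### The Aim 1 sensitivity analysis ignores the self-report of quitters who return no sample, so it could not expose a difference between arms in sample return

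*Combined protocol and SAP*

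**What the plan says.** Section 9.1 states: "The primary study outcome is biochemically-verified self-reported 7-day point prevalence abstinence at 6 months". A self-report without a sample cannot meet that definition. Section 5.9 makes the consequence explicit: "Participants who are unable to biochemically verify abstinence will be assumed to be smoking". That sentence stands under the continuous-abstinence item, but the 9.1 definition leads to the same place for the primary endpoint.

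For people who are not reached, section 9.1 says that "persons lost to follow up will be treated as non-abstinent". It then adds that "sensitivity analyses will consider a range of possible odds ratios (1, 2, and 5) linking loss to follow-up and smoking". Section 5.9 attaches the same three odds ratios to its sentence on unverified participants, again worded in terms of loss to follow-up.

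Section 4.0 allows a close relative who "can opt to complete a survey on the participant's behalf as a proxy". No rule says how proxy-reported abstinence without a sample enters the sensitivity analysis.

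Self-reported abstinence is collected at 1, 3, 6 and 12 months (Table 2). Section 9.1 specifies no comparison of it by arm, and no report of sample return by arm.

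**The concern.** Verified abstinence is the product of two things: the proportion who report quitting, and the proportion of those who return a sample that passes. If return differs between arms, the primary comparison mixes the two. Section 5.9 expects difficulty in obtaining samples, section 5.8 says that patients and research staff are unblinded, and the test route depends on current use of nicotine products, which may differ by arm. A gap is therefore possible, though nothing shows that one will occur.

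A sensitivity analysis should show whether the result depends on how unverified quitters are handled. A person who answered the survey and reported quitting is not lost to follow-up in the ordinary sense, and is far more likely to be abstinent than an average participant. An analysis that leaves this person as a smoker, or gives them the average odds, cannot show how much of the effect comes from sample return. The distortion can run either way: it can create an effect or hide one.

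**Working it through.** **1. The plan's own figure.** Section 9.1: "Conservatively assuming a biochemically validated abstinence rate of 10% under UC, a chi-squared test on 1000 patients" "will detect a MIST abstinence rate of 16.2"% with 80% power. The test is "tested at a 5% significance level via a chi-squared test with Yates' continuity correction". Allocation is not stated; I assume 1:1, 500 per arm. Exact enumeration of the Yates-corrected test gives 80.8% power for 10% vs 16.2%. The stated power is sound. With equal rates of 10%, the test rejects in 3.8% of trials.

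**2. Inputs for the illustration.**
- Survey reach of 80% in each arm, taken from the pilot in section 3.0: 400 reached and 100 lost per arm.
- Assumed: 20% of all randomised self-report abstinence in both arms, which is 100 people per arm and no true effect.
- Assumed: all tested samples pass.
- Assumed: sample return of 50% under UC and 60% under MIST.

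**3. Primary analysis.** Verified rate = self-reported rate × return rate.
- UC: 0.20 × 0.50 = 10% (50 people).
- MIST: 0.20 × 0.60 = 12% (60 people).
- RR = 12/10 = 1.20. Rejection probability is 14.7%.
- With a 5-point gap (50% vs 55%) the rates are 10% vs 11%, and rejection is 6.5%.

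**4. Planned sensitivity analysis.** Odds of abstinence in the missing = odds in the observed ÷ OR.

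*Losses only.* Observed: 50/400 and 60/400; missing: 100 per arm.
- OR 1: 50 + 100 × 0.125 = 62.5; 60 + 100 × 0.15 = 75.0; RR 1.20.
- OR 2: 56.7 vs 68.1; RR 1.20.
- OR 5: 52.8 vs 63.4; RR 1.20.

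*Unverified quitters pooled with losses, at the odds of everyone observed.* Observed: 50/350 and 60/360; missing: 150 and 140.
- OR 1: 50 + 150 × 0.1429 = 71.4; 60 + 140 × 0.1667 = 83.3; RR 1.17.
- OR 2: 61.5 vs 72.7; RR 1.18.
- OR 5: 54.8 vs 65.4; RR 1.19.

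The planned odds ratios leave most of the false effect in place under either reading.

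**5. Using the self-report.** Impute the unverified quitters from the pass rate among tested quitters, and keep the true losses non-abstinent. With all samples passing, this gives 100 vs 100, RR 1.00. For a less favourable case, let 80% of tested samples pass (odds 4). The primary RR is still 1.20 (40 vs 48 verified).
- OR 1: 40 + 50 × 0.80 = 80; 48 + 40 × 0.80 = 80; RR 1.00.
- OR 2: odds 4/2 = 2, probability 0.667; 73.3 vs 74.7; RR 1.02.
- OR 5: odds 4/5 = 0.8, probability 0.444; 62.2 vs 65.8; RR 1.06.

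**6. The opposite direction.** Take the design effect of 10% vs 16.2% with 60% return in both arms. If MIST return falls to 50%, the MIST verified rate becomes 16.2% × 50/60 = 13.5%, and power falls from 80.8% to 36.8%.

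**The case against.** Several points on the other side stand.

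- **Scope of the odds ratios.** The section 5.9 sentence begins with unverified participants and then turns to the odds ratios, so it can be read as applying them to everyone unverified. A reader might infer that the plan definitely restricts them to losses. The text does not settle this. The point above holds under both readings, provided that the reference odds are those of everyone observed. If the odds ratio were applied conditional on self-report, the plan would already be close to the fix, but neither section says so.
- **Other Aim 1 measures.** A reader might infer that every Aim 1 analysis is affected. That is too broad. Table 2 lists self-report as an Aim 1 measure, and section 5.9 adds initial abstinence and initial lapse with no stated verification requirement. The ancillary study in section 5.9 compares survey and EHR smoking status with biochemical validation. However, section 9.1 specifies no arm comparison of self-report, so the gap is narrower, not closed.
- **No evidence of a gap.** The collection routes and the $100 payment per time point are described without distinction by arm. Unequal staff effort is only an inference from the lack of blinding. A 5-point gap raises rejection only to 6.5%.
- **Self-report is not a clean benchmark.** Patients are unblinded. If true abstinence were equal but 15% vs 18% reported quitting, a test on self-report would reject in 22% of trials. Self-report should supplement the verified endpoint, not replace it.

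Counting unverified quitters as smokers is conventional for the primary analysis, and nothing here argues against it.

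**Conclusion.** The point holds as an inexpensive improvement. The primary rule and the stated power need no change. The weakness is that the sensitivity analysis, on either reading at the overall odds, does not use the self-report of unverified quitters and so would hardly respond to unequal sample return. In the illustration, a 10-point gap yields RR 1.20 and 14.7% rejection against 3.8% with no gap, and the sensitivity RRs stay between 1.17 and 1.20.

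These sizes rest on assumed return rates, 1:1 allocation, equal and equally truthful self-report in both arms, and all tested samples passing. A reader might infer that the trial is likely to show a false benefit for MIST. The documents do not support that: they give no return rate and no sign of a difference, and a gap in the other direction would hide a benefit.

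**What to change.** Keep the primary rule. In section 9.1, for both 6 and 12 months:

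1. State that the sensitivity analysis treats unverified self-reported quitters as their own missing class, separate from true losses. Include proxy-reported abstinence without a sample in this class. Impute abstinence conditional on self-report, from the pass rate among tested quitters, and vary it over the odds ratios 1, 2 and 5 already chosen.
2. Report the sample-return rate among self-reported quitters by arm.
3. Report self-reported 7-day abstinence by arm with a relative risk and confidence interval, labelled supportive only because patients are unblinded and self-report may itself be biased.

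The cost is a few sentences of SAP text and analyses of data already being collected. The downside is a few more supportive results to report.

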- a. This composite clinical outcome will be assessed by passive query of the VUMC EHR, the Tennessee Medicaid (TennCare) database, and the Department of Health Hospital Discharge Data System. The composite variable includes any evidence of a documented incident inpatient hospitalization, ER visit, or death during the follow up period. Death will be defined as death due to any cause as determined by National Death Index or death certificate data from Tennessee State Vital Record Files. Cause-specific mortality will be determined via death certificates obtained from the Tennessee State Vital Records, which has death certificates for all deaths in Tennessee and for Tennessee residents who die in adjoining states. Passive surveillance of 12-month clinical composite outcomes takes place at VUMC and non-VUMC facilities, as described further below.
 - i. At VUMC facilities. Hospitalization and ER visits at VUMC are tracked by Drs. [name] and [name], leveraging VCREATE and V-SERCH Center resources including validated EHR algorithms to extract clinical outcomes including ER visits, hospitalizations and mortality.
 - ii. At non-VUMC facilities. We have established links between VUMC EHR data and external databases including Tennessee Medicaid and the Hospital Discharge Data System (TN-HDDS). The TN-HDDS collects patient-level discharge information in visits from all hospitals licensed by the Tennessee Department of Health (TN DOH), including rehabilitation hospitals, psychiatric units within acute care hospitals, and free-standing ambulatory surgical treatment centers. Tennessee Medicaid (TennCare) maintains an extensive electronic data system and records of all their healthcare encounters, including pharmacy prescriptions filled.
- b. Vital status may be ascertained by study staff reviewing VUMC medical records, utilizing automated electronic health record (EHR) deceased notifications, conducting obituary searches, participant proxy contacts, and PCP/provider offices. Death certificate data from the Tennessee Office of Vital Records may also be used to identify all deaths occurring within Tennessee, and deaths of Tennessee residents that occur in surrounding states. Vanderbilt's Health Policy Department processes these data for research and public health surveillance activities via data use agreements with the TN DOH. Finally, data from the National Death Index or related databases that include information on mortality may be queried.

MIST Ancillary study - Validation of EHR-derived smoking status with survey and biochemically-validated smoking abstinence in the MIST RCT: If EHRderived self-reported outcomes were valid, then large health care systems and their EHRs could become a new frontier for tobacco control including large observational studies and multisite pragmatic clinical trials. Smoking cessation RCTs conducted within a health system thus offer a unique opportunity to determine the accuracy of smoking status as captured in the EHR.

- a. **AIM 1**: Using biochemical validation as the reference for abstinence at 6 months, determine the reliability of EHR-based and survey sources of smoking status among MIST trial participants. Hypothesis: EHR based smoking status and research survey smoking status will have a high sensitivity, specificity, positive predictive value and negative predictive value as compared to biochemical validation among participants in the MIST study.
- b. **AIM 2**: Demonstrate the application of EHR-based smoking status in analyses of the impact of NMR-guided prescribing practice on smoking cessation in the MIST trial. **Hypothesis**: EHR-based smoking status may be incorporated into analyses that use smoking abstinence as an outcome (e.g., 7-day point prevalence abstinence (PPA) at 6 months, the primary outcome of the MIST parent trial) through either an extension of existing multiple imputation methods or through direct use of EHR-based smoking status as an outcome.

The ability to leverage electronic health records for tobacco and cancer related research would allow investigators to efficiently and powerfully examine the role of smoking, smoking cessation and cancer among diverse populations, including people actively attempting to change their smoking behavior.

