5.10 Compensation

Participants can be compensated up to a total of \$430 for full participation in this research study. Participants will receive \$10 for the screening blood draw and \$40 for completion of the baseline survey. For completion of the follow up surveys at 1, 3, 6, and 12 month study timepoints participants will receive \$20 per survey. In addition to survey completion, participants who report quitting smoking on the 6 and 12 month surveys will be asked to provide either a saliva sample or complete a CO test, used for biochemical validation of self-reported abstinence. For completion of biochemical validation at the 6 and 12 month timepoints, participants will receive \$100 per timepoint. \$50 will be offered for travel reimbursement at each of the 6 and 12 month timepoints. Similar compensation has been used in a previous research studies and was deemed by the VUMC Institutional Review Board (IRB) to be an appropriate, non-coercive, amount of funds for involvement in a clinical research project.

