The informed consent document will state clearly to patients that the study is being done as a collaboration between VUMC and TelASK, a company that makes automated phone calls. Subjects will be informed that in order to make the phone calls, TelASK will be given information such as their name, study ID, phone number, sex, preference for time of call, and the date that they are discharged from the hospital or enrolled. During the study, TelASK will establish a secure website to view call results in real time, quit status, and "on-demand" counseling requests. Data will be transferred to TelASK via HIPAA-compliant secure FTP. This plan is consistent with what the VUMC IRB has approved for our ongoing NIH funded study of hospitalized smokers (5R01HL11182107: PIs [name] and [name]). Upon completion of the study, data will be transmitted back to VUMC's secure password-protected computer system. All patient data will be purged from TelASK's data files.

Data Security and Confidentiality – Samples

Blood samples used for NMR will be collected and labeled using information such as the study participant number, and/or MRN and stored in a secure location until NMR analysis is conducted by Vanderbilt Pathology Laboratory Services (VPLS), ARUP (currently contracts with VUMC) or other equivalent laboratory.

Blood or saliva for future analyses of genetics and other potentially relevant biological markers will be collected, de-identified, and stored in a secure location, in the laboratory of [name] in Light Hall. Salivary cotinine/CO samples collected for biochemical validation of self reported abstinence will be labelled with study participant number.

| Construct | Measures | Source | Baseline timepoint (CSF, | 1 | 3 | 6 | 12 |
|------------------|--|----------|--------------------------|---|---|---|----|
| | | | RASF, Baseline survey) | m | m | m | m |
| | | | | | | | |
| Sociodemographic | Age, sex, education, race/ethnicity, employment, living | Patient | Х | | | | |
| Factors | situation, health insurance type | | | | | | |
| Medical | Pre-existing condition – VACS [53]; WHI Extension | Patient/ | Х | | | | |
| Condition/Pre- | Study, HIV/AIDS [54] (Coronary heart disease, chronic | EHR/Pr | | | | | |
| existing | obstructive pulmonary disease, stroke, cancer, | оху | | | | | |
| Conditions | hypertension, diabetes, hyperlipidemia) | | | | | | |
| Checklist | Pregnancy | | Х | Х | Х | Х | Х |
| | | | | | | | |

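### Ancillary Aim 1 promises four accuracy measures against biochemical validation, but only self-reported quitters are sampled: for the survey only PPV is estimable, and for the EHR the reference set is not fixed

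*Combined protocol and SAP*

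**What the plan says.** The ancillary study is described in section 5.9. Its Aim 1 is set up "Using biochemical validation as the reference for abstinence at 6 months", with the task to "determine the reliability of EHR-based and survey sources of smoking status among MIST trial participants". The hypothesis is that "EHR based smoking status and research survey smoking status will have a high sensitivity, specificity, positive predictive value and negative predictive value". No threshold for high is given, and no sample size or accuracy figure.

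Four places bear on who has a reference result:

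- Section 4.0 asks for a CO or cotinine test "to confirm quit smoking status if they indicate on the survey that they have quit smoking".
- Section 5.9, under biochemical verification, says: "For participants who self-report abstinence at the 6 month and/or 12 month follow up surveys, study staff will attempt to biochemically-verify the self-report".
- Section 5.10 says that "participants who report quitting smoking on the 6 and 12 month surveys will be asked to provide either a saliva sample", with a CO test as the alternative.
- Section 10.3 describes the samples as "collected for biochemical validation of self reported abstinence will be labelled with study participant number".

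Nothing provides for testing self-reported smokers, a random subsample of them, or survey non-responders. No correction for partial verification is stated. The only rule for people without verification is the parent trial's convention (sections 5.9 and 9.1), which counts unverified and lost participants as smoking.

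**The concern.** Sensitivity, specificity, PPV and NPV need a reference result on both sides of the source being judged. Here the survey answer decides who gets the reference test, so the survey is judged against a reference that exists only where the survey says quit. Several of the promised figures would then be fixed by the sampling rule, whatever the truth about the survey.

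The EHR is a separate source, so its table is not empty in the same way. It still inherits the selection: measured reference results exist only for people who told the survey that they had quit. The ancillary study is presented as evidence on whether EHR smoking status is accurate enough for large observational studies and pragmatic trials, so it matters whether its accuracy figures describe the cohort, a selected fraction of it, or an assumption.

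**Working it through.** The documents give no accuracy figure to reproduce. The check is structural, followed by an illustration. Abstinent is the positive class, in line with the aim's wording. If smoking were the positive class, the labels would swap but the same row would be empty.

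**Survey, tested set.** TP = reported quit and confirmed; FP = reported quit and not confirmed. No self-reported smoker is tested, so FN = TN = 0.

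- Sensitivity = TP/(TP + 0) = 100%
- Specificity = 0/(FP + 0) = 0%
- NPV = 0/0, undefined
- PPV = TP/(TP + FP), the only measure that data can inform

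**Survey, untested counted as smokers.** FN = 0 by rule, so sensitivity and NPV are both 100%. Specificity rests on the assumption. PPV becomes confirmation rate × return rate. With assumed confirmation of 70% to 90% and assumed return of 60% to 80%, PPV runs from 0.7 × 0.6 = 42% to 0.9 × 0.8 = 72%, against 70% to 90% among returned samples.

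**How many have a measured reference.** Section 9.1 gives 10% (UC), 16.2% (MIST) and 1,000 patients; 500 per arm is my assumption.

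- Verified abstinent: 500 × 0.10 + 500 × 0.162 = 131
- Tested at 90% and 70% confirmation: 131/0.9 = 146; 131/0.7 = 187
- No measured reference: 1,000 − 146 = 854 (85%); 1,000 − 187 = 813 (81%)
- Tested and not confirmed: 146 − 131 = 15; 187 − 131 = 56

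**EHR, reference confined to the tested set.** Specificity would rest on those 15 to 56 people, all of whom reported quitting when the test says otherwise. To see the effect, take these assumed inputs, none of them in the documents: 1,000 people, true abstinence 13.1% (131/1,000), survey sensitivity 98%, 5% of smokers misreporting, all self-reported quitters tested, EHR sensitivity 70%, and an EHR false-abstinent rate of 10% in honest smokers and either 10% or 50% in misreporters.

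Tested: 131 × 0.98 + 869 × 0.05 = 128.4 + 43.5 = 172.

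| EHR measure | Misreporters 10%: cohort | tested | Misreporters 50%: cohort | tested |
|---|---|---|---|---|
| Sensitivity | 70% | 70% | 70% | 70% |
| Specificity | 90% | 90% | 88% | 50% |
| PPV | 51% | 95% | 47% | 81% |
| NPV | 95% | 50% | 95% | 36% |

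Example, 10% case, tested NPV: TN = 43.5 × 0.9 = 39.1; FN = 128.4 × 0.3 = 38.5; 39.1/(39.1 + 38.5) = 50%. Varying true abstinence over 10% to 16.2% and misreporting over 5% to 10%, tested-set NPV is 31% to 73% against 94% to 96% in the cohort. Sensitivity does not move, because nearly all true abstainers are tested and EHR recording was taken as independent of the survey among them.

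**EHR, untested counted as smokers.** All four measures can be computed. In the illustration the reference has 1,000 − 131 = 869 smokers, of whom 813 to 854 (94% to 98%) are assumed, not measured.

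**Bounds that are available.** Let q be true abstinence among self-reported smokers, taken as 0% to 3%, and treat the 813 to 854 untested people as self-reported smokers. Survey NPV = 1 − q = 97% to 100%. Survey sensitivity at q = 3% is 131/(131 + 0.03 × 854) = 131/156.6 = 84%, or 131/(131 + 0.03 × 813) = 131/155.4 = 84%; at q = 0 it is 100%.

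**The case against.** The strongest reply concerns the EHR. The aim speaks of trial participants in general, and the trial's verified-abstinence variable is defined for everyone. On that reading, EHR specificity rests mostly on self-reported smokers, nearly all of whom probably do smoke, and the remaining error comes mainly from unreturned samples and non-responders. This stands. A reader might infer that EHR specificity is estimated only in misreporters; that is true only if the analysis is confined to returned samples, which the aim does not say.

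A reader might also infer that every EHR measure is distorted. Sensitivity is little affected if nearly all true abstainers report quitting and return samples; in the tested set the main problems are specificity, NPV and PPV.

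Third, a reader might suppose that Aim 1's figures feed ancillary Aim 2, which proposes EHR status for imputation or as an outcome. The text does not say that Aim 2 uses Aim 1's estimates. Nor is there a pass mark in the hypothesis.

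Finally, if bounds are good enough for the EHR they are good enough for the survey. This also stands, so survey sensitivity, specificity and NPV need not be removed if they are shown as bounds.

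None of this rescues the survey hypothesis as written: no reading of the sampling rule yields a data-based estimate of survey sensitivity, specificity or NPV.

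**Conclusion.** The point holds. For the survey, three of the four hypothesised measures cannot be learned from the data to be collected, and following the plan would produce values set by the sampling rule or by the smoking convention. This needs no outside assumption. For the EHR, the conclusion is conditional: the aim must say whether the reference is the tested set, where specificity, NPV and PPV do not carry over to the cohort, or the trial-defined outcome, where most of the reference is assumed.

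The counts show scale and are not forecasts. The documents give neither confirmation nor return rates, 16.2% is a detectable rate rather than an expected one, and equal allocation is assumed. The defect is confined to the ancillary study. The parent trial's primary endpoint needs verification only of claimed abstinence, so its analysis is unaffected.

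**What to change.** Amend ancillary Aim 1 in section 5.9:

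1. **Survey.** Make PPV among returned samples the only directly estimated measure. Drop the hypothesis of high sensitivity, specificity and NPV, or report these only as bounds under a stated range of true abstinence among self-reported smokers (for example 0% to 3%).
2. **EHR.** Report agreement in the tested set, labelled as conditional on self-reported abstinence. Add whole-cohort sensitivity, specificity, PPV and NPV as an assumption-based sensitivity analysis over the same range. A Begg-Greenes correction cannot do this alone, because no self-reported smoker is verified.
3. **Missing reference.** For this aim, treat self-reported quitters without a sample as having a missing reference, not as smokers, and state how survey non-responders are handled.

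The cost is rewording one aim, a small extra analysis and a narrower claim. No new samples are needed. Estimating the missing measures from data would require testing some self-reported smokers, which is a larger change than this point calls for.
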